589 The recruitment will take place at Maastro. The patient will have at least 3 days of time to
590 consider participation in the trial, however a period much longer than 3 days will interfere
591 with normal clinical workflows and risk delaying urgently needed treatment. Therefore, the
592 subject will be contacted after 3 days by the TPA. The TPA will ensure that the patient
593 understands the content of the study, that all the patient's questions are answered, and the
594 patient is willing to participate in the study. The TPA will verify whether the patient

595 understands what participation in the trial entails by asking them to repeat in their own
596 words what the participation means. If the patient decides to participate in the trial, they will
597 give verbal consent to plan the additional scan. Prior to this scan, an appointment will be
598 planned for the patient and TPA to discuss any questions of the patients regarding the trial
599 and to sign the Informed Consent form. The participant must personally sign and date the
600 latest approved version of the Informed Consent form before any trial specific procedures
601 are performed.

602

603 The written and verbal versions of the Participant Information and Informed Consent that
604 are presented to the participants will detail no less than: the exact nature of the trial; what
605 participation in the trial will involve for the participant; the implications and constraints of
606 the protocol and any risks involved in taking part. It will be clearly stated that the participant
607 is free to withdraw from the trial at any time for any reason without prejudice to future care,
608 and with no obligation to give the reason for withdrawal.

609

610 Written Informed Consent will then be obtained by means of a dated participant signature
611 and a dated signature of the person who presented and obtained the Informed Consent.
612 The TPA will, together with the clinical trial coordinator, ensure that the informed consent
613 is correctly and fully signed and dated by the participant and included in the study
614 documentation at the research department of Maastro before any study-related procedures
615 take place. The person who obtains the consent must be suitably qualified and experienced
616 and have been authorized to do so by the Principal Investigator. The participant will also
617 receive an original of the signed informed consent form. The signed form will be retained
618 at the trial site.

619

620 **11.3 Objection by minors or incapacitated subjects (if applicable)**

621 Not applicable.

622

623 **11.4 Benefits and risks assessment, group relatedness**

624 Additional imaging is performed on the novel cone-beam CT imaging device using x-rays.
625 There is no direct benefit for the individual patients. Additional radiation exposure is only a
626 small fraction (<0.1%) of the radiation received during their standard radiotherapy
627 treatment. Collected data will not be used for clinical decision making. If the novel CBCT
628 images provide new information that may lead to improved treatment, the findings will be
629 communicated to the treating physician but need verification using standard imaging
630 procedures.

631

632 **11.5 Compensation for injury**

633 The sponsor has a liability insurance which is in accordance with article 7 of the WMO. The
634 sponsor (also) has a clinical trial insurance which is in accordance with the legal
635 requirements in the Netherlands (Article 7 WMO). This insurance provides coverage for
636 damage to research subjects through injury or death caused by participation in the study.
637 The insurance applies to the damage that becomes apparent during the study or within 4
638 years after the end of the study.

639

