Secondary objective: Qualitative assessment will be performed for the patient categories receiving 2 different novel CBCT imaging modes. Stage II-IV lung cancer patients stage (II-IV) receive a 60 seconds free breathing CBCT acquisition and a 6 seconds breath hold CBCT acquisition. Breast, stage I lung cancer stage I and abdominal cancer patients receive a 6 seconds breath hold and a 6 seconds free-breathing CBCT acquisition. A head-to-head comparison of image quality between the 2 modes of novel CBCT image acquisition will also be performed. At least 2 radiation oncologists and 2 radiation therapists will be asked to rank the suitability of

294 the images for RT image guidance and for treatment planning on a 5-point Likert
295 scale, with specific assessments for each of the anatomical locations included in the
296 study (as defined in previous secondary endpoint).

297
298 In all analyses where a novel CBCT is compared to a standard CBCT, the standard
299 CBCT will be taken from the subject's radiation treatment fraction that was delivered
300 on the same day as the novel CBCT image acquisition. Therefore, the only additional
301 imaging is the novel CBCT.

302
303 **8.1.3 Other study parameters (if applicable)**
304 Not applicable

305
306 **8.2 Randomisation, blinding and treatment allocation**

307 No randomisation will be performed.

308
309 **8.3 Study procedures**

310 Patients will be recruited from the standard radiotherapy population. Patients will be asked
311 to undergo an additional imaging session on the novel cone-beam CT imaging system
312 during which 1 or 2 additional CBCT images will be acquired. The additional imaging
313 session will be performed on one of the subject's standard treatment days to limit additional
314 travel and burden on the patients.

315
316 The exact technical details of the additional imaging session depend on the anatomical
317 region to be investigated, as described below.

318
319 For head-and-neck patients: one additional extended cone-beam CT scan will be
320 performed. The extended CBCT consists of (typically 2) sequential cone-beam CT scans
321 that are automatically stitched together to create a full field-of-view of the treated region.

322
323 For stage I lung cancer patients: two additional cone-beam CT scans will be acquired. The
324 first cone-beam CT scan will be performed under conditions of free-breathing. An additional

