325 cone-beam CT scan will be acquired with the subject performing a breath hold.

326
327 For stage II-IV lung cancer patients: two additional cone-beam CT scans will be acquired.
328 Both cone-beam CT scans will be performed under conditions of free-breathing. The first
329 cone-beam CT will be a fast (6 second) cone-beam CT. The second CBCT will be a slow
330 scan (approximately 60 seconds in duration) that will be used to evaluate novel motion
331 compensation algorithms.

332
333 For left breast cancer patients: one additional breath hold cone-beam CT scan will be
334 acquired.

336 For pelvic cancer patients: one additional cone-beam CT scan will be acquired under
337 conditions of free breathing.

338

339 For abdominal cancer patients: two additional cone-beam CT scans will be acquired. The
340 first cone-beam CT scan will be performed under conditions of free-breathing. An additional
341 cone-beam CT scan will be acquired with the subject performing a breath hold.

342

343 All cone-beam CT scans will be acquired using the vendor-supplied default imaging mode
344 for the anatomical region being imaged.

345

346 **8.4 Withdrawal of individual subjects**

347 Subjects can withdraw from the study at any time for any reason if they wish to do so. The
348 decision to withdraw from the study will not result in any consequences for the subject. The
349 investigator can decide to withdraw a subject from the study if the investigator decides that
350 continuation in the study may be harmful to the subject. Data collected until the time of
351 withdrawal will be used for analysis, unless the patient requests that the data is destroyed.

352

353 **8.4.1 Specific criteria for withdrawal (if applicable)**

354 Not applicable

355

356 **8.5 Replacement of individual subjects after withdrawal**

357 Subjects who withdraw before their novel CBCT imaging session has occurred will be
358 replaced by new subjects as long as the inclusion numbers are not exceeded.

359

360 **8.6 Follow-up of subjects withdrawn from treatment**

361 No follow-up is foreseen after withdrawal.

362

363 **8.7 Premature termination of the study**

364 Premature termination of the study will occur if:

- 365 - The approval of the competent medical ethics review committee that assessed the
366 research is irrevocably withdrawn;
- 367 - It appears that the continuation of the research cannot serve a scientific purpose, and

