517 commercially available treatment planning system (Varian Eclipse).

518

519 **Secondary objective:** Qualitative assessment of novel CBCT vs. standard cone-beam CT
520 imaging system from radiation oncologists and therapists. Qualitative assessment of the
521 novel CBCT images will be obtained by presenting individual novel CBCT images as well
522 as head-to-head comparisons of novel and standard CBCT images from the same patient
523 (if available). At least 2 radiation oncologists and 2 radiation therapists will be asked to rank
524 the suitability of the images for RT image guidance and for treatment planning on a 5-point
525 Likert scale, with specific assessments for each of the anatomical locations included in the
526 study.

527

528 Besides a rating of the image quality in terms of overall quality impression, specific
529 questions will be tailored for the different anatomical areas:

530 - Head and neck: contrast between tumour and organs at risk; sufficiency of imaging
531 volume; reduction of artifacts (e.g., due to dental fillings), where applicable.

532 - Lung cancer (stage I): Identification and delineation of the tumour

533 - Lung cancer (stage II-IV): Identification of structures of interest in the mediastinal region
534 (organs-at-risk, primary tumour and possible involved lymph nodes).

535 - Left breast cancer: Identification and delineation of structures of interest; sufficiency of
536 imaging volume; reduction in metal artifacts (where applicable).

537 - Abdominal cancers: Identification and delineation of structures of interest; reduction in
538 air/tissue interface artifacts.

539 - Pelvic cancers: Identification and delineation of structures of interest; reduction in
540 air/tissue interface artifacts; reduction in metal artifacts (where applicable).

541

542 **Secondary objective:** Qualitative assessment will be performed for the patient categories
543 receiving 2 different novel CBCT imaging modes. Stage II-IV lung cancer patients stage
544 receive a 60 seconds free breathing and a 6 seconds breath hold CBCT acquisition. Breast,
545 stage I lung cancer and abdominal cancer patients receive a 6 seconds breath hold and 6
546 seconds free-breathing CBCT acquisition. A head-to-head comparison of image quality
547 between the 2 modes of novel CBCT image acquisition will also be performed. At least 2
548 radiation oncologists and 2 radiation therapists will be asked to rank the suitability of the

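### Scan order is fixed in the three two-scan cohorts, so the two-mode comparison estimates mode plus any second-scan effect

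*Combined protocol and SAP*

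**What the plan says.** Section 2 makes the comparison of two acquisition modes of the novel system a secondary objective: breath hold against free breathing, or fast against slow. Section 8.3 sets out how the scans are taken:

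- **Stage I lung:** the "first cone-beam CT scan will be performed under conditions of free-breathing. An additional" "cone-beam CT scan will be acquired with the subject performing a breath hold".
- **Abdomen:** the paragraph opens "For abdominal cancer patients: two additional cone-beam CT scans will be acquired. The" and then repeats the stage I lung wording, so free breathing again comes first.
- **Stage II-IV lung:** "Both cone-beam CT scans will be performed under conditions of free-breathing. The first" "cone-beam CT will be a fast (6 second) cone-beam CT. The second CBCT will be a slow" scan of about 60 seconds.
- **Left breast:** "For left breast cancer patients: one additional breath hold cone-beam CT scan will be" acquired, so there is no order to speak of. Head-and-neck and pelvis also have one acquisition.

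Section 8.2 says that nothing is randomised. No section alternates the order, repeats a mode or adjusts for order. Sections 8.1.2 and 10.2 have at least two radiation oncologists and two radiation therapists score the two modes head to head on a 5-point scale. Section 10.2 plans no tests for this, only descriptive statistics and 95% confidence intervals.

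The endpoint sections do not list the same scans as 8.3. Section 10.2 says that stage II-IV lung patients "receive a 60 seconds free breathing and a 6 seconds breath hold CBCT acquisition. Breast" and the text continues "stage I lung cancer and abdominal cancer patients receive a 6 seconds breath hold and 6" seconds free breathing. Section 8.1.2 says the same in substance. So breast has two modes there and one scan in 8.3, and the 6-second stage II-IV scan is a breath hold there and free breathing in 8.3.

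**The concern.** In a within-patient comparison of two scans from one session, the patient is the control, and what remains is whatever differs between the scans. Here two things differ in every pair: the mode and the position in the session. If the second scan is systematically better or worse for reasons unrelated to mode, that difference is credited to breath hold (stage I lung, abdomen) or to the slow acquisition (stage II-IV lung). Possible reasons are settling on the couch, bowel gas moving between scans, or tiring. These are conjectures. The protocol discusses motion and air-tissue artefacts, but within a scan, not between two scans.

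What is at stake is how clearly one secondary result can be read. A reported preference for a mode, with its interval, would be taken as a property of the mode.

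**Working it through.** **The plan's own figure.** No sample size is given for the two-mode comparison. The only calculation (section 4.4) is 40 patients for a paired effect size of 0.45 on the primary endpoint. With two-sided 0.05 and an assumed 80% power (power is not stated), ((1.960 + 0.842)/0.45)² = 38.8, so 39 by the normal approximation and 41 by the t distribution. The figure is reproduced well enough, and nothing below depends on it.

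**How many patients.** Section 4.4 gives 40 patients, six sites and at least 5 per site. Section 8.3 describes two scans at three sites.

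- Minimum: 3 × 5 = 15.
- Maximum: 40 − 3 × 5 = 25, with the other three sites at their minimum.

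**What the comparison estimates.** Let *m* be the mode effect (second-listed mode minus first) and *s* the effect of being the second scan. Under the order in 8.3, each patient's difference has expectation *m* + *s*. So does the mean over any number of patients. Any *s* passes one for one into the mode estimate.

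The design matrix shows the same. Take the minimum 15 patients: 10 with free breathing and breath hold, 5 with fast and slow. There are 15 patient intercepts, a breath-hold column, a slow column and a second-scan column, 18 in all. Under the fixed order the breath-hold and slow columns add up to the second-scan column, so the rank is 17. With orders split 5/5 and 3/2 the rank is 18 and all effects can be estimated.

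**What the interval covers.** For a mean paired difference the 95% half-width is t(0.975, n−1)/√n, in units of the SD of the paired difference:

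| n | half-width (SD) |
|---|---|
| 5 | 1.24 |
| 15 | 0.55 |
| 25 | 0.41 |

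These reflect sampling error only; *s* is not in them. The rows for 15 and 25 assume pooling over cohorts, which mixes two contrasts. In a single cohort of five, sampling error is large, and a modest *s* would be small beside it.

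**What alternation does.** In patients scanned in the listed order the mode difference has expectation *m* + *s*; in those scanned in reverse it is *m* − *s*. The average of the two order-specific means is *m*. The variance relative to a simple mean is (n/4)(1/n₁ + 1/n₂):

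- n = 5, split 2/3: (5/4)(1/2 + 1/3) = 1.042.
- n = 15, split 7/8: (15/4)(1/7 + 1/8) = 1.004.
- n = 25, split 12/13: (25/4)(1/12 + 1/13) = 1.002.

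The average must be over the two order means. A simple mean over a 2/3 split would still carry (3 − 2)/5 = 0.2 of *s*.

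**Why not odd and even study IDs.** Section 12.1 gives one sequential inclusion number for the whole trial, so parity does not alternate within a cohort. If parity is random, a cohort of five has all one order with probability 2/32 = 6.25%, and a 4/1 split or worse with probability 12/32 = 37.5%. The chance that at least one of three such cohorts has a single order is 1 − 0.9375³ = 18%.

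**The case against.** The strongest reply is that the aliasing is shown but an order effect is not. The documents give no figure for one, and even its direction is open: settling would favour the second scan and tiring would harm it. Both scans come from one session. The comparison is secondary, carries no test, and sits in a study meant for initial assessments, so a sentence of limitation in the report could be enough. All of this stands, and it sets the weight of the point.

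Three stronger readings are tempting, and the documents do not support them.

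- A reader might infer that a preference cannot be attributed to the mode at all. That would need evidence of an order effect large enough to explain the preference, and there is none.
- A reader might infer that fixed order does damage through missing scans, because a shortened session always loses the same mode. A head-to-head pair is lost whichever scan is missing, so alternation recovers no pairs. The documents give no rate of shortened sessions. Section 1 expects a single breath hold to be feasible for most patients, not all, so failed breath holds follow mode under any order.
- A reader might infer that the primary result is affected. The primary endpoint compares the novel system with standard CBCT and with the planning CT, which is not the contrast between the two novel modes.

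Descriptive status does not dispose of the point entirely. Intervals are planned, and they will be read as uncertainty about the mode difference.

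**Conclusion.** The point holds as a modest design improvement. In stage I lung, abdomen and stage II-IV lung, 15 to 25 patients, mode and scan position are completely aliased under section 8.3. The head-to-head comparison therefore estimates mode plus any second-scan effect, and the planned 95% intervals do not show it. More patients would not remove it.

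The conclusion rests on section 8.3 being what is carried out, on enrolment of 40 with at least 5 per site, and on both scans being completed. The size of the bias cannot be given: it equals an order effect whose size and sign are unknown and which may be small. The number of affected cohorts and the content of the stage II-IV contrast stay unsettled until 8.3 is reconciled with 8.1.2 and 10.2. On the wording of the endpoint sections, the stage II-IV comparison would also mix speed with breathing condition.

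**What to change.** In section 8.3, alternate the acquisition order by enrolment sequence within each two-scan cohort, from a per-cohort list. Take the order actually used from the acquisition time that section 12.1 already puts on the case report form. In section 10.2, state that the mode difference is the average of the two order-specific means. If a fixed order is operationally necessary, give the reason and report the contrast as mode plus order.

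In the same edit, reconcile section 8.3 with 8.1.2 and 10.2 on which scans the breast and stage II-IV lung cohorts receive.

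The cost is an order list for the operator and a small protocol change; if made after the favourable opinion, section 12.3 requires that it be communicated to the METC. No extra scan, patient or staff is needed, and the precision lost is about 4% in variance for a cohort of five and less for larger ones. Alternation cancels a constant order effect. It does not remove an order-by-mode interaction.

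### For stage II-IV lung and left breast, the scans acquired under section 8.3 do not form the pairs that sections 8.1.2 and 10.2 say will be compared

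*Combined protocol and SAP*

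**What the plan says.** Section 8.3 (Study procedures) sets out what is acquired at each site. For stage II-IV lung it lists two scans: "Both cone-beam CT scans will be performed under conditions of free-breathing". The first "cone-beam CT will be a fast (6 second) cone-beam CT. The second CBCT will be a slow" "scan (approximately 60 seconds in duration". For left breast it lists one: "For left breast cancer patients: one additional breath hold cone-beam CT scan will be" acquired.

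Section 8.1.2 defines a secondary endpoint that compares two novel CBCT modes within the same patient. It says that stage II-IV lung patients "receive a 60 seconds free breathing CBCT acquisition and a 6 seconds breath hold CBCT acquisition", and then: "Breast, stage I lung cancer stage I and abdominal cancer patients receive a 6 seconds breath hold and a 6 seconds free-breathing CBCT acquisition".

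Section 10.2 repeats this in the analysis text. Stage II-IV lung patients "receive a 60 seconds free breathing and a 6 seconds breath hold CBCT acquisition. Breast" is the first word of the next sentence, which continues: "stage I lung cancer and abdominal cancer patients receive a 6 seconds breath hold and 6" seconds free-breathing.

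Section 2 states the objective as breath hold against free breathing, or 6-second against 60-second acquisition, according to which scans a patient receives. It assigns no tumour sites to either contrast. Section 4.4 sets 40 patients, with at least 5 at each of six sites. Section 10.2 restricts the analysis of this endpoint to descriptive statistics and 95% confidence intervals.

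**The concern.** Section 8.3 tells site staff what to acquire; sections 8.1.2 and 10.2 tell the analyst what to compare. For two sites these instructions cannot both be carried out, and the document gives no rule for which section prevails.

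The consequences differ by site. For left breast, following 8.3 leaves no second scan, so the stated comparison cannot be made. For stage II-IV lung a pair exists under either version, but its meaning changes. Under 8.3 the two scans differ in speed, with breathing condition held the same. Under 8.1.2 and 10.2 they differ in both, and a difference in reader scores could not be attributed to speed alone. This matters for section 2 because stage II-IV lung is the only site for which any section lists a 60-second novel scan, so the whole fast-against-slow objective rests on it.

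A missing scan could not be recovered within the protocol: section 8.3 provides one additional imaging session, and section 9.4 ends participation with it. Breast patients would also have one or two research scans depending on which section staff follow.

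**Working it through.** The plan gives no figure to reproduce here. The check sets the sections side by side and then bounds the number of patients involved.

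**Step 1. Scans by site**

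| Site | Section 8.3 | Sections 8.1.2 and 10.2 | Agree? |
|---|---|---|---|
| Stage II-IV lung | 6 s free-breathing; about 60 s free-breathing | 60 s free-breathing; 6 s breath hold | No: breathing condition of the 6 s scan |
| Left breast | one breath hold | 6 s breath hold; 6 s free-breathing | No: one scan or two |
| Stage I lung | free-breathing; breath hold | 6 s breath hold; 6 s free-breathing | Yes, on number and breathing condition |
| Abdomen | free-breathing; breath hold | 6 s breath hold; 6 s free-breathing | Yes, on number and breathing condition |
| Head and neck | one extended scan | not named | No conflict |
| Pelvis | one free-breathing | not named | No conflict |

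So 2 of the 4 sites named in the endpoint conflict, or 2 of 6 overall. At each of the two, one scan of the pair does not conflict: the 60-second free-breathing scan for lung and the breath-hold scan for breast (8.3 gives no duration for the latter).

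**Step 2. Does section 2 settle it?** It defines its groups by the scans received. Under both versions stage II-IV lung patients receive a 6-second and a 60-second scan, so they belong to the fast-against-slow group either way. Under 8.1.2 and 10.2 they also meet the definition of the breath-hold against free-breathing group. Section 2 therefore fits both versions and decides nothing.

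**Step 3. Patients affected** (inputs from section 4.4: N = 40, minimum 5 per site, six sites)

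- Places fixed by the minimums: 6 × 5 = 30. Unallocated: 40 − 30 = 10.
- Two affected sites, lowest: 2 × 5 = 10, and 10/40 = 25%.
- Two affected sites, highest: 10 + 10 = 20, and 20/40 = 50%. This needs all 10 unallocated places to go to these two sites.

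**Step 4. Pairs available as the endpoint sections state them**

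| Pair in 8.1.2 and 10.2 | If 8.3 is followed | If 8.1.2 and 10.2 are followed |
|---|---|---|
| Breast: breath hold vs free-breathing | 0 | at least 5 |
| Stage II-IV lung: 60 s free-breathing vs 6 s breath hold | 0 | at least 5 |

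The lung zero refers to that exact pair; a 6-second against 60-second pair, both free-breathing, would still exist under 8.3. The figure of at least 5 assumes that every listed scan is obtained.

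**The case against.** The strongest counter-arguments concern weight, not the contradiction itself.

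- *Only one scan per pair conflicts, and lung keeps a usable pair.* This is correct. The loss is total for breast but is a change of contrast for lung, and the two should not be read as equal. The pair compared is still not the pair acquired at either site.
- *The endpoint limits itself to patients who receive two modes, so breast would simply drop out under 8.3.* The opening sentence of the endpoint can be read that way, but the same paragraph goes on to name breast among the sites receiving two scans. The conflict remains.
- *The numbers are soft.* The 50% figure is an extreme allocation. The minimum of 5 pairs is also not assured where a breath hold is needed, since section 1 expects a single breath hold to be feasible for most patients, not all. Both caveats stand.
- *Little depends on it.* The endpoint is secondary and descriptive, the images do not alter treatment, and both versions stay within the one or two additional scans covered by the risk text in section 13.1. All of this stands and limits the severity. On the other side, section 10.1 computes CNR on every acquired image, so which scans exist also bears on the data available for the primary parameter.

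A text-extraction fault is an unlikely explanation: the sentences on each side are complete, and the endpoint version appears in both 8.1.2 and 10.2.

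**Conclusion.** The concern holds with high confidence, because it rests on reading current sections against each other and on no statistical assumption. For stage II-IV lung and left breast the document does not settle which images are acquired or which contrast is reported. Half of the sites in the two-mode endpoint are affected, holding 25% to 50% of the planned 40 patients on the assumption that 40 are enrolled and the site minimums are met. No error rate, planned test or sample size basis changes. It should be fixed, but it does not threaten the primary comparison as designed.

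**What to change.** Reconcile sections 2, 8.1.2, 8.3 and 10.2 into one acquisition list per tumour site, giving number of scans, scan time and breathing condition. Which schedule is intended is for the sponsor and investigator to state; this review takes no position on it.

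Then:

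- have the two-mode endpoint name only the sites and scan pairs on that list;
- label the stage II-IV lung contrast by what actually differs between its two scans: speed, breathing condition, or both. If both differ, say that a fast-against-slow reading under section 2 must be made with caution.

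The cost is a protocol amendment to wording. No additional patients are needed.
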